#### **Grade 2** hyperthyroidism events (and **Grade 2-4** hypothyroidism):

In hyperthyroidism, non-selective beta-blockers (e.g. propranolol) are suggested as initial therapy.

In hypothyroidism, thyroid hormone replacement therapy, with levothyroxine or liothyronine, is indicated per standard of care.

#### **Grade 3-4** hyperthyroidism

Treat with an initial dose of IV corticosteroid followed by oral corticosteroids. When symptoms improve to Grade 1 or less, steroid taper should be started and continued over no less than 4 weeks. Replacement of appropriate hormones may be required as the steroid dose is tapered.

### **Hepatic:**

For **Grade 2** events, monitor liver function tests more frequently until returned to baseline values (consider weekly).

Treat with IV or oral corticosteroids

For **Grade 3-4** events, treat with intravenous corticosteroids for 24 to 48 hours.

When symptoms improve to Grade 1 or less, a steroid taper should be started and continued over no less than 4 weeks.

### **Renal Failure or Nephritis:**

For **Grade 2** events, treat with corticosteroids.

For **Grade 3-4** events, treat with systemic corticosteroids.

When symptoms improve to Grade 1 or less, steroid taper should be started and continued over no less than 4 weeks.

**Management of Infusion Reactions:** Signs and symptoms usually develop during or shortly after drug infusion and generally resolve completely within 24 hours of completion of infusion.

Table 6 above shows treatment guidelines for subjects who experience an infusion reaction associated with administration of pembrolizumab (MK-3475).

**Table 6: Infusion Reaction Treatment Guidelines**

NCI CTCAE Grade	Treatment	Premedication at subsequent dosing

Grade 1 Mild reaction; infusion interruption not indicated; intervention not indicated
	
Increase monitoring of vital signs as medically indicated until the subject is deemed medically stable in the opinion of the investigator.
	
None

Grade 2 Requires infusion interruption but responds promptly to symptomatic treatment (e.g., antihistamines, NSAIDs, narcotics, IV fluids); prophylactic medications indicated for < =24 hrs
	
Stop Infusion and monitor symptoms. Additional appropriate medical therapy may include but is not limited to:
 
 
• IV fluids
 
• Antihistamines
 
• NSAIDS
 
• Acetaminophen
 
• Narcotics
 
 
Increase monitoring of vital signs as medically indicated until the subject is deemed medically stable in the opinion of the investigator. If symptoms resolve within one hour of stopping drug infusion, the infusion may be restarted at 50% of the original infusion rate (e.g., from 100 mL/hr to 50 mL/hr). Otherwise dosing will be held until symptoms resolve and the subject should be premedicated for the next scheduled dose.
 
Subjects who develop Grade 2 toxicity despite adequate premedication should be permanently discontinued from further trial treatment administration.
	
Subject may be premedicated 1.5h (± 30 minutes) prior to infusion of pembrolizumab (MK-3475) with:
 
Diphenhydramine 50 mg po (or equivalent dose of antihistamine).
 
Acetaminophen 500-1000 mg po (or equivalent dose of antipyretic).


Grades 3 or 4 Grade 3: Prolonged (i.e., not rapidly responsive to symptomatic medication and/or brief interruption of infusion); recurrence of symptoms following initial improvement; hospitalization indicated for other clinical sequelae (e.g., renal impairment, pulmonary infiltrates) Grade 4: Life-threatening; pressor or ventilatory support indicated
	
Stop Infusion. Additional appropriate medical therapy may include but is not limited to:
 
 
• IV fluids
 
• Antihistamines
 
• NSAIDS
 
• Acetaminophen
 
• Narcotics
 
• Oxygen
 
• Pressors
 
• Corticosteroids
 
• Epinephrine
 
 
Increase monitoring of vital signs as medically indicated until the subject is deemed medically stable in the opinion of the investigator. Hospitalization may be indicated.
 
Subject is permanently discontinued from further trial treatment administration.
	
No subsequent dosing

NCI CTCAE Grade	Treatment	Premedication at subsequent dosing
Appropriate resuscitation equipment should be available in the room and a physician readily available during the period of drug administration.		

## 5.7. Diet/Activity/Other Considerations

### 5.7.1. Diet

Subjects should maintain a normal diet unless modifications are required to manage an AE such as diarrhea, nausea or vomiting.

### 5.7.2. Contraception

Pembrolizumab may have adverse effects on a fetus *in utero*. Furthermore, it is not known if pembrolizumab has transient adverse effects on the composition of sperm.

For this trial, male subjects will be considered to be of non-reproductive potential if they have azoospermia (whether due to having had a vasectomy or due to an underlying medical condition).

Female subjects will be considered of non-reproductive potential if they are either:

postmenopausal (defined as at least 12 months with no menses without an alternative medical cause; in women < 45 years of age a high follicle stimulating hormone (FSH) level in the postmenopausal range may be used to confirm a post-menopausal state in women not using hormonal contraception or hormonal replacement therapy. In the absence of 12 months of amenorrhea, a single FSH measurement is insufficient.);

OR

have had a hysterectomy and/or bilateral oophorectomy, bilateral salpingectomy or bilateral tubal ligation/occlusion, at least 6 weeks prior to screening;

OR

has a congenital or acquired condition that prevents childbearing.

Female and male subjects of reproductive potential must agree to avoid becoming pregnant or impregnating a partner, respectively, while receiving study drug and for 120 days after the last dose of study drug by complying with one of the following contraception regimens if sexually active:

Single method (one of the following is acceptable):

- intrauterine device (IUD)
- vasectomy of a female subject's male partner
- contraceptive rod implanted into the skin

Combination method (requires use of two of the following):

- diaphragm with spermicide (cannot be used in conjunction with cervical cap/spermicide)
- cervical cap with spermicide (nulliparous women only)
- contraceptive sponge (nulliparous women only)
- male condom or female condom (cannot be used together)
- hormonal contraceptive: oral contraceptive pill (estrogen/progestin pill or progestin-only pill), contraceptive skin patch, vaginal contraceptive ring, or subcutaneous contraceptive injection

Subjects should be informed that taking the study medication may involve unknown risks to the fetus (unborn baby) if pregnancy were to occur during the study. In order to participate in the study subjects of childbearing potential must adhere to the contraception requirement (described above) from the day of study medication initiation (or 14 days prior to the initiation of study medication for oral contraception) throughout the study period up to 120 days after the last dose of trial therapy. If there is any question that a subject of childbearing potential will not reliably comply with the requirements for contraception, that subject should not be entered into the study.

### **5.7.3. Use in Pregnancy**

If a subject inadvertently becomes pregnant while on treatment with pembrolizumab, the subject will immediately be removed from this study and followed on an alternative hematology branch protocol (eg: 94-H-0010). The site will contact the subject at least monthly and document the subject's status until the pregnancy has been completed or terminated. The outcome of the pregnancy will be reported to the IRB and to Merck without delay and within 24 hours to the Sponsor and within 2 working days to Merck if the outcome is a serious adverse experience (e.g., death, abortion, congenital anomaly, or other disabling or life-threatening complication to the mother or newborn).

The study investigator will make every effort to obtain permission to follow the outcome of the pregnancy and report the condition of the fetus or newborn to the Sponsor. If a male subject impregnates his female partner the study personnel at the site must be informed immediately and the pregnancy reported to the IRB and to Merck and followed as described section 9.1.3.

### **5.7.4. Use in Nursing Women**

It is unknown whether pembrolizumab is excreted in human milk. Since many drugs are excreted in human milk, and because of the potential for serious adverse reactions in the nursing infant, subjects who are breast-feeding are not eligible for enrollment.

## 5.8. Subject Withdrawal/Discontinuation Criteria

Subjects may withdraw consent at any time for any reason or be dropped from the trial at the discretion of the investigator should any untoward effect occur. In addition, a subject may be withdrawn by the investigator or the Sponsor if enrollment into the trial is inappropriate, the trial plan is violated, or for administrative and/or other safety reasons.

### 5.8.1. Off-Treatment Criteria

A subject must be discontinued *from treatment* for any of the following reasons:

- Unacceptable adverse experiences as described in Section 5.2
- Any grade 4 treatment-emergent adverse event
- Intercurrent illness that prevents further administration of treatment
- The subject has completed 35 cycles of pembrolizumab (ie: induction and continuation phase)
- The subject or legal representative (such as a parent or legal guardian) withdraws consent for treatment.
- Investigator's decision to withdraw the subject from treatment

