## 5.2. Dose Modification Guidelines For Drug-Related Adverse Events

### 5.2.1. Hematologic toxicities

Given the pathobiology of Acute Myeloid Leukemia, severe blood count abnormalities (up to grade 4 levels in leukocytes, neutrophils, lymphocytes, red blood cells and platelets) are expected and may be present at baseline.

Decitabine will be initiated on Cycle 1 and 3 regardless of peripheral blood count values. After this point, if hematologic recovery (absolute neutrophil count  $\geq 1,000/\mu\text{L}$  and platelets  $\geq 50,000/\mu\text{L}$ ) does not occur six weeks after initiation of prior cycle of decitabine in complete remission patients, then subsequent decitabine doses will be modified to consist of five days of 20mg/m^2 given, at the discretion of the investigator, anytime during days 8-19 of a cycle.

In accordance with the FDA label and past clinical trial experience no dose modification will be made for pembrolizumab in the event of hematological toxicity.

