	Grade 4	Permanently discontinue		
fever) and of bowel perforation (ie, peritoneal signs and ileus).
 
 
• Participants with <math>\geq</math> Grade 2 diarrhea suspecting colitis should consider GI consultation and performing endoscopy to rule out colitis.
 
• Participants with diarrhea/colitis should be advised to drink liberal quantities of clear fluids. If sufficient oral fluid intake is not feasible, fluid and electrolytes should be substituted via IV infusion.
 

AST / ALT elevation or Increased bilirubin	Grade 2	Withhold	
 
• Administer corticosteroids (initial dose of 0.5- 1 mg/kg prednisone or equivalent) followed by taper
 
	
 
• Monitor with liver function tests (consider weekly or more frequently until liver enzyme value returned to baseline or is stable
 

	Grade 3 or 4	Permanently discontinue	
 
• Administer corticosteroids (initial dose of 1-2 mg/kg prednisone or equivalent) followed by taper
 
	
Type 1 diabetes mellitus (T1DM) or Hyperglycemia	Newly onset T1DM or Grade 3 or 4 hyperglycemia associated with evidence of $\beta$ -cell failure	Withhold	
 
• Initiate insulin replacement therapy for participants with T1DM
 
• Administer anti-hyperglycemic in participants with hyperglycemia
 
	
 
• Monitor participants for hyperglycemia or other signs and symptoms of diabetes.
 

Hypophysitis	Grade 2	Withhold	
 
• Administer corticosteroids and initiate hormonal replacements as clinically indicated.
 
	
 
• Monitor for signs and symptoms of hypophysitis (including hypopituitarism and adrenal insufficiency)
 

	Grade 3 or 4	Withhold or permanently discontinue 		
Hyperthyroidism	Grade 2	Continue	
 
• Treat with non-selective beta-
 
	
 
• Monitor for signs and symptoms of thyroid
 

	Grade 3 or 4	Withhold or permanently discontinue 	blockers (eg, propranolol) or thionamides as appropriate	disorders.

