Hypothyroidism	Grade 2-4	Continue	
 
Initiate thyroid replacement hormones (eg, levothyroxine or liothyronine) per standard of care
 
	
 
Monitor for signs and symptoms of thyroid disorders.
 

Nephritis and Renal dysfunction	Grade 2	Withhold	
 
Administer corticosteroids (prednisone 1-2 mg/kg or equivalent) followed by taper.
 
	
 
Monitor changes of renal function
 

	Grade 3 or 4	Permanently discontinue		
Myocarditis	Grade 1 or 2	Withhold	
 
Based on severity of AE administer corticosteroids
 
	
 
Ensure adequate evaluation to confirm etiology and/or exclude other causes
 

	Grade 3 or 4	Permanently discontinue		
All other immune-related AEs	Intolerable/persistent Grade 2	Withhold	
 
Based on type and severity of AE administer corticosteroids
 
	
 
Ensure adequate evaluation to confirm etiology and/or exclude other causes
 

	Grade 3	Withhold or discontinue based on the type of event. Events that require discontinuation include and not limited to: Gullain-Barre Syndrome, encephalitis		
	Grade 4 or recurrent Grade 3	Permanently discontinue		

1. Withhold or permanently discontinue pembrolizumab is at the discretion of the investigator or treating physician.
 
NOTE: For participants with Grade 3 or 4 immune-related endocrinopathy where withhold of pembrolizumab is required, pembrolizumab may be resumed when AE resolves to ≤ Grade 2 and is controlled with hormonal replacement therapy or achieved metabolic control (in case of T1DM).
				

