### 9.1.2. Severity

The descriptions and grading scales found in the revised NCI Common Terminology Criteria for Adverse Events (CTCAE) version 4.03 will be utilized for grading the *severity* (intensity) of **non-hematologic** AEs (<http://ctep.cancer.gov/reporting/ctc.html>).

Given the pathobiology of Acute Myeloid Leukemia, severe blood count abnormalities (up to grade 4 levels in leukocytes, neutrophils, lymphocytes, red blood cells and platelets) are expected and may be present at baseline. Thus we will record these values in the protocol database, but will not report these abnormalities as adverse or serious adverse events unless the grade of toxicity (based on NCI-Common Terminology Criteria for Adverse Events, CTCAE v4.0) is grade 4 or above and was not present at baseline. If the myelosuppressive event is fatal (Grade 5), or if the Investigator finds the event to be medically important, then it will be collected as an SAE.

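### The mandatory stop in section 5.8.1 for any grade 4 treatment-emergent event contradicts section 5.2.1 for new grade 4 cytopenias and Table 5 for grade 4 hypothyroidism, and nothing says which prevails

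*Combined protocol and SAP*

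**What the plan says.** Section 5.8.1 lists reasons for which a subject has to come off treatment. One is "Any grade 4 treatment-emergent adverse event". It is not limited by organ system, expectedness or relatedness.

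Section 5.2.1 deals with haematologic toxicity. It expects abnormalities up to grade 4 in every blood line and allows that they may already be there at baseline. It then says "Decitabine will be initiated on Cycle 1 and 3 regardless of peripheral blood count values". Later decitabine is shortened, not stopped, when counts fail to recover in patients in complete remission. For the other drug, "no dose modification will be made for pembrolizumab in the event of hematological toxicity".

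Section 9.1.2 keeps cytopenias out of adverse-event reporting unless the toxicity "is grade 4 or above and was not present at baseline".

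Table 5 sets the pembrolizumab action for immune-related events. Its hypothyroidism row reads "Hypothyroidism Grade 2-4 Continue". The row for "Newly onset T1DM or Grade 3 or 4 hyperglycemia associated with evidence of" beta-cell failure says to withhold. Grade 3 or 4 hypophysitis and hyperthyroidism carry "Withhold or permanently discontinue". A closing note adds: "For participants with Grade 3 or 4 immune-related endocrinopathy where withhold of pembrolizumab is required, pembrolizumab may be resumed when AE resolves to" grade 2 or lower, provided the condition is controlled.

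**The concern.** A patient who develops a new grade 4 neutropenia or thrombocytopenia in cycle 1 must stop under 5.8.1. Under 5.2.1 the same patient goes on to pembrolizumab in cycle 2 and decitabine in cycle 3. Both texts are written as instructions, and the event is one the protocol itself expects.

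The primary objective is feasibility, reported as a description of adverse events. The text that was applied decides how much drug an affected patient received, what stop reason was recorded, whether continuing (or stopping) was a protocol deviation, and how long the patient was observed. If patients were handled under different readings, or the reading is not stated, the feasibility description mixes the regimen's tolerability with the choice of rule.

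**Working it through.** **Side by side**

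| Event | 5.8.1 | Specific text | Relation |
|---|---|---|---|
| Grade 4 cytopenia already present at baseline | Not treatment-emergent on the ordinary meaning (the term is not defined) | 5.2.1 continues; 9.1.2 does not report it | No conflict |
| New grade 4 cytopenia | Stop | 5.2.1 continues; 9.1.2 reports it as an adverse event | Contradiction |
| Grade 4 hypothyroidism | Stop | Table 5: continue | Contradiction |
| Grade 4 hyperglycaemia with beta-cell failure | Stop | Table 5: withhold; note allows resumption | Option removed |
| Grade 4 hypophysitis or hyperthyroidism | Stop | Table 5: withhold or discontinue, at discretion | Option removed |

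**Is there a precedence rule?** Three candidates fail.
- The first bullet of 5.8.1 cites section 5.2, but as a separate reason to stop; it does not limit the grade 4 bullet.
- Section 5.3 says that timings may change under 5.2. That covers timing only.
- Section 8.3 excludes haematological toxicity, but only from the Bayesian safety endpoint.

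Reading treatment-emergent as treatment-related would not help either: drug-caused cytopenia and immune-related hypothyroidism would still be caught.

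**How many patients?** The documents give no rate for new grade 4 cytopenia. Purely as an assumption, let q be the proportion of 10 patients affected. The expected number is 10q, and the chance of at least one is 1 − (1 − q)^10:
- q = 0.10: 1 patient; 0.651
- q = 0.30: 3 patients; 0.972
- q = 0.50: 5 patients; 0.999

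Section 2.5.2 gives grade 3 or 4 neutropenia in 87% on decitabine. That is in MDS, on another schedule and with both grades combined, so it is only a high-end reference.

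For hypothyroidism, section 11.2.1 gives serious events in 0.1% of 1562 subjects: 10 × 0.001 = 0.01 expected, or 15 × 0.001 = 0.015 at maximum accrual. Seriousness is not grade and the population differs, so this is a rough guide.

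**What changes for one affected patient?** This assumes full planned dosing and a patient who would otherwise complete induction.
- Induction: 8 × 21 = 168 days; 8 pembrolizumab doses; decitabine 10 days × 4 cycles = 40 days; response marrows after cycles 2, 4, 6 and 8.
- Stop at end of cycle 1: 1 of 8 doses and 10 of 40 days. The last dose is on day 19, so the safety visit falls near day 19 + 30 = 49. That is 168 − 49 = 119 days earlier (119/168 = 71%). None of the 4 scheduled on-treatment marrows has been reached.
- Stop at end of cycle 4: 4 of 8 doses and 20 of 40 days. The last dose is pembrolizumab on day 3 × 21 + 1 = 64, so the visit falls near day 94. That is 74 days earlier (74/168 = 44%). Two of the 4 marrows have been reached.

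The visit comes sooner still if new anti-cancer treatment starts first.

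**What does the earlier visit cut off?** Section 6.5.1 stops collection of new adverse-event information at the safety visit. Sections 9.4 and 9.6 separately keep serious events and events of clinical interest reportable to 90 days after cessation, or earlier if new therapy starts. Counting from the last dose, that is about day 19 + 90 = 109 for a cycle 1 stop and day 64 + 90 = 154 for a cycle 4 stop. Persistent treatment-related events and ongoing serious events are also followed past the visit (6.5.1, 9.1.1). The 119 and 74 days therefore apply only to new events that are neither serious nor of clinical interest.

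**The case against.** The strongest reply is that little hangs on this. The study closed to accrual on November 30, 2017 and has been in data analysis only since March 15, 2019 (section 11.3), so new wording cannot alter anyone's treatment. No test, threshold or sample size depends on the conflict. That stands. It limits the remedy to wording and reporting, but does not remove the contradiction or its effect on stop reasons and deviations.

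The reply also stands against several stronger inferences that a reader might draw:
- **That safety data in general end 30 days after an early stop.** They do not: the 90-day windows and the follow-up of persistent events remain.
- **That a non-responder who is stopped must leave the study.** One bullet of 5.8.2 points that way, because active surveillance is open only to patients in complete or partial remission. The closing paragraph of 5.8.2, however, gives disease-status follow-up to those who stop for reasons other than progression. The outcome is unclear, not settled.
- **That an early stop leaves no response assessment.** Scheduled on-treatment marrows after the stop are missed. Section 6.3 (with Table 7), Appendix E and Appendix G still provide an off-treatment or off-study response assessment.
- **That every endocrine entry in Table 5 contradicts 5.8.1.** Only hypothyroidism does; elsewhere 5.8.1 removes an option.

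**Conclusion.** The contradiction is real and unresolved. It is flat for new grade 4 cytopenias, which the protocol itself makes foreseeable, and for grade 4 hypothyroidism, which is probably rare. It bears on exposure, recorded stop reasons, deviation status and length of observation. The number of patients affected cannot be determined from the documents. The per-patient figures are illustrations that rest on full dosing and otherwise completed induction.

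A reader might infer that the feasibility analysis or the safety stopping rule is invalid. The documents do not support that: the Table 7 summary can be reported under either reading, and the section 8.3 endpoint excludes haematological toxicity and stays computable. This is worth fixing because it is cheap and touches the primary description. It takes no position on which clinical rule is right.

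**What to change.** Reconcile the grade 4 bullet of 5.8.1 with 5.2.1, 9.1.2 and the endocrine entries of Table 5, so that one instruction applies to each event, and say whether unrelated grade 4 events are covered. The choice of clinical rule belongs to the sponsor.

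Since only analysis remains, also:
- state in the analysis which text was applied;
- classify stop reasons and deviations consistently with it;
- list each grade 4 treatment-emergent event by type (haematologic, endocrine, other), baseline grade, whether treatment continued, and the date adverse-event collection ended.

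The cost is a wording change, one statement and one listing covering at most 15 patients. No procedures or patients are added.

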### 5.8.2. Off-Study Criteria

A subject must be removed *from the study* for any of the following reasons:

- Confirmed disease progression despite at least two cycles of hypomethylating agent therapy and/or four doses of pembrolizumab. For these purposes disease progression is defined as greater than 50% relative increase in blasts in the peripheral blood or bone marrow or development of extramedullary disease (see Appendix A) at a therapy response assessment time-point (see Appendix G) compared to before start of treatment or relapse in those previously in complete remission (mCR/mCRi, CR/CRi).
- Patient meets off-treatment criteria but is not eligible, or declines, active surveillance phase
- The subject has a confirmed positive serum pregnancy test
- Subject becomes significantly noncompliant with study drug administration, study procedures, or study requirements, which might increase risk or substantially compromise the interpretation of study results.
- The subject is lost to follow-up
- The subject completes two years on study
- Administrative reasons
- The subject or legal representative (such as a parent or legal guardian) withdraws consent
- Investigator's decision to withdraw the subject from the study

The end of treatment and follow-up visit procedures are listed in Section 6.

The End of Treatment and Follow-up visit procedures are listed in Section 6. After the end of treatment, each subject will be followed for 30 days for adverse event monitoring. Subjects who discontinue for reasons other than progressive disease will have post-treatment follow-up for disease status until disease progression, initiating another cancer treatment, withdrawing consent or becoming lost to follow-up. After study withdrawal each subject will be offered the opportunity to consent to an alternative hematology branch protocol (eg: 94-H-0010) to allow follow-up by telephone at approximately three monthly intervals for overall survival until death, withdrawal of consent, or the closing of the study protocol, whichever occurs first.

